| End of treatment                                 | _                        |                            |    |    |    |        |            |     |     |          |     |     | X   |               |
| End of trial                                     |                          |                            |    |    |    |        |            |     |     |          |     |     |     | X             |

ADA = anti-drug antibodies; AE = adverse event; BMI = body mass index; DEXA = dual-energy x-ray absorptiometry; ECG = electrocardiogram; EoT = End of Treatment; FSH = follicle-stimulating hormone; HbA1c = hemoglobin A1c; HIV = human immunodeficiency virus; in-house = hospital admission at site; PGIC = patient's global impression of change; PK = pharmacokinetics; PS = parenteral support; SBS = short bowel syndrome; SBS-I = SBS impact scale; SBS-IF = SBS with intestinal failure; WOCBP = women of childbearing potential

<sup>13 Patients to receive instructions orally and in writing.

<sup>14 Trial product administration at visit 9 according to treatment schedule.

<sup>15 Questionnaires must be completed at site visits prior to any other trial related assessment. It is recommended that the PGIC is completed first, followed by the SBS-I, then the EQ-5D 5L. All PROs are to be completed during treatment as indicated in the flowchart.

Flowchart for 48-hour Metabolic Balance Study

|                                       | 48-hour n                 | netabolic balance study          | (Visit 1 and Visit 9 | 9)                      |
|---------------------------------------|---------------------------|----------------------------------|----------------------|-------------------------|
| Procedures                            | Day 1                     | Day 2                            | Day 3                | Day 4                   |
| Admission to hospital                 | X                         |                                  |                      |                         |
|                                       | (≥ 16 hours prior to      |                                  |                      |                         |
|                                       | metabolic balance samples |                                  |                      |                         |

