|                                       | collection start)         |                                  |                      |                         |
| Confirmation of eligibility           | X (Visit 1 only)          |                                  |                      |                         |
| Adverse events                        | X                         | X                                | X                    | X                       |
| Concomitant medication                | X                         | X                                | X                    | X                       |
| Physical examination                  | X                         |                                  |                      |                         |
| ECG (12-lead)                         | X                         |                                  |                      |                         |
| Vital signs (blood pressure, pulse    | X                         | X                                | X                    | X                       |
| rate, temperature)        |                           |                                  |                      |                         |
| Body weight               | X                         | X                                | X                    | X                       |
| Biochemistry                          | X                         |                                  |                      |                         |
| Hematology                            | X                         |                                  |                      |                         |
| Urinalysis                            | X                         |                                  |                      |                         |
| Serum pregnancy test (WOCBP           | X                         |                                  |                      |                         |
| only)                                 |                           |                                  |                      |                         |
| Citrulline                            | X                         |                                  |                      |                         |
| PK, see Table 3                       | X                         | X (Visit 9 only)                 | X (Visit 9 only)     | X (Visit 9 only)        |

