|                                       |                           |                                  |                      | (48h from start $\pm 1$ |
|                                       |                           |                                  |                      | hour)                   |
| Confirm drinking menu                 | X (Visit 1 only)          |                                  |                      | ·                       |
| Fixed oral fluid intake               | •                         | X                                | X                    | X                       |
| Define baseline PS type, volume,      | X (Visit 1 only)          |                                  |                      |                         |
| content                   | •                         |                                  |                      |                         |
| DEXA scan                 |                           | X                                |                      |                         |
| PGIC                                  |                           | X (Visit 9 only)                 |                      |                         |
| SBS-I                                 |                           | X                                |                      |                         |
| EQ-5D-5L                              |                           | X                                |                      |                         |
| Luminal- and mucosa-associated        | X                         |                                  |                      |                         |
| microbiota                |                           |                                  |                      |                         |
| Adjustment of PS (at visit 9 only, if |                           |                                  |                      | X                       |
| applicable)                           |                           |                                  |                      |                         |
| Trial product administration          |                           |                                  |                      | X (Visit 1) 7           |
| Trial product dispensing              |                           |                                  |                      | X                       |

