| Hospital discharge                    |                           | <del> </del>                     |                      | X                       |

<sup>1 Body weight and vital signs will be performed at the same time point each day, in the morning prior to breakfast and by 08:00 (±2 hour).

<sup>2 ADA sample should be taken pre-dose at visit 1. At visit 9 the ADA sample should be taken as long time after last dose as possible and before next dosing during the admission.

 Metabolic Balance Study (MBS).

<sup>4 Based on current weekly average PS volume.

<sup>5 DEXA scan may be done on Day 2 or Day 3 to allow for study site flexibility.

<sup>6 To be collected after 12:00 – preferably as close to 12:00 as possible. To be frozen at -80°C as fast as possible.

<sup>7 Trial product administration at visit 9 according to treatment schedule.

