### **8.2.17** Patient Reported Outcomes

The PGIC, SBS-I and EQ-5D-5L (36). PROs will be used to investigate the effects of treatment on health-related quality of life.

Questionnaires must be completed in paper format at site visits, see Table 1, prior to any other trial-related assessment. The PROs will be completed by the patient without assistance of site personnel.

• When all 3 questionnaires are to be completed at a visit, patients are recommended to first complete the PGIC followed by the SBS-I and the EQ-SD-5L.

\_

<sup>1 Blood samples for analyses of HbA1c will only be collected for patients who reach Week 4 after protocol amendment #2 has become effective.

• When only the SBS-I and EQ-5D-5L are to be completed at a visit, it is recommended that the SBS-I is completed first.

The PROs must not be completed at home before the patient attends the visit (however, see also COVID-19 Management, section 8.1.7). Patients will be instructed to complete the PROs in a private area without influence from site personnel or accompanied by family or friends. No one is allowed to answer or interpret items for the patient. The Investigator or a delegated site personnel is allowed to read items/answers options to the patient aloud if the patient is unable to read. The Investigator or delegated site personnel will instruct the patient to complete every item in the PROs and explain that there are no right or wrong answers. The Investigator or a delegated site personnel will instruct the patient to give the best answer they can and explain that all responses will remain confidential.

Immediately after completion, the PROs will be reviewed by the Investigator (or designee) for completeness and potential AEs. When reviewing the PROs for AEs the Investigator should not influence nor question the patient on the content of their response to PRO questions. Review of the PROs must be documented. If entries are missing in the PROs, the patient should be asked to answer all questions. Care should be taken not to bias the patient.

The Investigator and/or delegated site personnel will receive training and instruction in completion of the PROs prior to the conduct of the trial.

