Each item is rated on a discrete scale from 0 to 10. Each SBS-I item score will be analyzed overall and separately for patients with SBS-II and patients with SBS-IF at Baseline, Week 12, Week 24 and Week 52 (EOT). Changes from baseline to Week 12, Week 24 and Week 52 (EOT) are calculated as described in Section 2.1.2 and will be analyzed at Week 12, Week 24 and Week 52 (EOT).

The EQ-5D-5L has five domains (mobility, self-care, usual activities, pain/discomfort, anxiety/depression) with the following five response levels: no problems (1), slight problems (2), moderate problems (3), severe problems (4), and unable to/extreme problems to do something (5). Additionally, the current health should be assessed on a visual analogue scale between 0 and 100.

Furthermore, an EQ-5D-5L index value summarizing the values from all domains will be analyzed. It is calculated based on the Danish standardisation study for the EQ-5D-5L (Jensen, C.E. et al. The Danish EQ-5D-5L Value Set: A Hybrid Model Using cTTO and DCE Data. Appl Health Econ Health Policy 19, 579–591 (2021). https://doi.org/10.1007/s40258-021-00639-3). If all domain values are non-missing, it is calculated using the following algorithm:

```
IF (mobility=1) THEN mo=0
IF (mobility=2) THEN mo=0.041
IF (mobility=3) THEN mo=0.054
IF (mobility=4) THEN mo=0.157
IF (mobility=5) THEN mo=0.220
IF (selfcare=1) THEN sc=0
IF (selfcare=2) THEN sc=0.035
IF (selfcare=3) THEN sc=0.050
IF (selfcare=4) THEN sc=0.144
IF (selfcare=5) THEN sc=0.209
IF (usual activities=1) THEN ua=0
IF (usual activities=2) THEN ua=0.033
IF (usual activities=3) THEN ua=0.040
IF (usual activities=4) THEN ua=0.139
IF (usual activities=5) THEN ua=0.174
IF (pain discomfort=1) THEN pd=0
IF (pain discomfort=2) THEN pd=0.048
IF (pain discomfort=3) THEN pd=0.094
IF (pain discomfort=4) THEN pd=0.381
IF (pain discomfort=5) THEN pd=0.537
IF (anxiety depression=1) THEN ad=0
IF (anxiety depression=2) THEN ad=0.072
IF (anxiety depression=3) THEN ad=0.191
IF (anxiety depression=4) THEN ad=0.430
IF (anxiety depression=5) THEN ad=0.618
total = mo + sc + ua + pd + ad
EQ5D5L Index Value = 1-total
```

In case any of the domain values is missing, the index value will be missing.

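### Table 2 places the baseline and Week 24 questionnaires on Day 2 of the admission, against the protocol's rule that they come first, so the Week 12 and Week 52 PRO changes carry an avoidable setting difference

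*Protocol*

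**What the plan says.** Footnote 15 to Table 1 (Protocol 1.2) is attached to the PGIC, SBS-I and EQ-5D-5L rows: "Questionnaires must be completed at site visits prior to any other trial related assessment". Those rows are marked at Visits 1, 6, 9, 12 and follow-up for SBS-I and EQ-5D-5L, and at Visits 6, 9 and 12 for PGIC. Protocol 8.2.17 gives the same instruction, that the questionnaires come "prior to any other trial-related assessment", and makes no exception for Visit 1 or Visit 9.

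Table 2, the schedule for the two in-house balance studies, puts SBS-I and EQ-5D-5L on Day 2 at both visits and PGIC on Day 2 at Visit 9. Day 1 already holds the physical examination, ECG, vital signs, body weight, blood and urine sampling, microbiota sampling and adverse event review. Admission is "≥ 16 hours prior to" the start of balance collection.

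The endpoints (Protocol 1.1 and Table 4; SAP 2.4) are changes in SBS-I and EQ-5D-5L from baseline to Weeks 12, 24 and 52, and PGIC at each of those weeks. SAP 4.3.4 analyses them descriptively.

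**The concern.** A site cannot follow both instructions at Visits 1 and 9. If it follows Table 2, the baseline is answered by an inpatient who has been through a day of procedures and a night on the ward. At Weeks 12 and 52 the same patient answers before anything else at an outpatient visit.

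Some content could respond to that. The SAP says of EQ-5D-5L that "the current health should be assessed on a visual analogue scale between 0 and 100", and one of its domains is usual activities. With a single open-label arm there is no control group in which a shift due to setting would also appear and could be subtracted. At stake is how far a reader can attribute a Week 12 or Week 52 PRO change to time on treatment rather than to where and when the questionnaire was filled in.

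**Working it through.** No sample size, power or alpha figure bears on this point. The check compares the schedules, with one clock calculation and one piece of algebra.

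**1. Is the Day 2 placement real, or a table-reading error?** In Table 2 the DEXA row has its mark in the same column as the three questionnaires. Its footnote says: "DEXA scan may be done on Day 2 or Day 3 to allow for study site flexibility". The column is therefore Day 2.

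**2. What precedes the questionnaires?** Balance collection starts at 08:00 on Day 2 (Protocol 8.2.1), and admission is at least 16 hours earlier:

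- 08:00 on Day 2 − 16 h = 16:00 on Day 1, the latest admission time.

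So one hospital night and the Day 1 assessments come before any Day 2 questionnaire. Table 2 gives no clock time within Day 2.

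**3. Setting at each time point.** Visit types are from Table 1. Let *h* be the effect on a score of answering in-house on Day 2, and *a* the effect of answering first at a site visit. Then

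observed mean change = true change + (setting effect at the visit − setting effect at baseline).

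| Time point | Visit type | Questionnaire timing | Setting term in the change |
|---|---|---|---|
| Baseline (V1) | In-house | Day 2 | reference, *h* |
| Week 12 (V6) | Site | Before other assessments | *a* − *h* |
| Week 24 (V9) | In-house | Day 2 | *h* − *h* = 0 |
| Week 52 (V12) | Site | Before other assessments | *a* − *h* |

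Two of the three planned changes contain *a* − *h*. At Week 24 it cancels.

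**4. PGIC.** It has no baseline value and is reported as a level. Week 24 carries *h*, while Weeks 12 and 52 carry *a*. Setting Week 24 beside either of the others brings in a difference of *h* − *a*. Weeks 12 and 52 are comparable with each other.

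**5. Which instruments are exposed?** All eight SBS-I items ask about the last week (SAP 2.4), so one hospital night is a small part of the recall period. The EQ-5D-5L scale asks about current health and is more open to the day's setting.

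**6. Is fasting part of the difference?** No. Table 1 requires fasting at Visits 1, 4, 6, 9, 12 and follow-up, so Visits 6 and 12 are fasting visits too. Table 2 ends the in-house fast when collection starts, and since the Day 2 questionnaires have no clock time, a fasted baseline is not established.

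**7. Size.** The documents give no standard deviation for any PRO and no inpatient–outpatient difference, so neither the size nor the sign of *a* − *h* can be computed.

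**The case against.** The best defence is textual. Table 1 separates site visits (S) from in-house visits (I), footnote 15 speaks of site visits, and Table 2 is the more specific schedule for the in-house stays. On that reading there is no contradiction.

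The reading is possible but weak. Table 1 attaches footnote 15 to rows that include Visits 1 and 9, and its abbreviation list describes in-house as an admission at the site. Protocol 8.1.7 counts site visits from Visit 2 onward, a range that includes Visit 9. Protocol 8.2.17 also gives an order for visits at which only SBS-I and EQ-5D-5L are completed, and in Table 1 those are Visit 1 and follow-up. Even if the reading is accepted, the setting difference remains.

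A second objection is to the remedy. Moving Visit 9 to Day 1 for a patient whose baseline was taken on Day 2 would break the Week 24 match, the one comparison that is now clean. In a trial of 6 to 16 patients, flagging listings would not repair that. This objection stands, and the fix allows for it. It is also true that admission may be as late as 16:00, before the 22:00 fast begins, so Day 1 answers may differ from Weeks 12 and 52 in time of day and fasting state. Moving the rows removes the procedures and the hospital night but does not make the occasions identical.

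A third objection is weight: the endpoints are exploratory, have no test or decision rule, and come from an open-label single-arm trial in which PRO changes already support little causal inference. That also stands, and it limits the severity.

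**Conclusion.** The point holds as a minor one, a cheap improvement. Table 2 conflicts with footnote 15 and Section 8.2.17. As scheduled, the Week 12 and Week 52 changes in EQ-5D-5L, and to a lesser degree SBS-I, include a setting difference of unknown size and direction. So does any comparison of PGIC at Week 24 with Weeks 12 and 52. The primary and key secondary results are not affected.

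A reader might infer more, and the documents do not support it:

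- That all PRO changes mix setting with treatment. The Week 24 change does not, because both readings are in-house on Day 2.
- That a fasting baseline is set against non-fasting follow-up. Fasting is also required at Visits 6 and 12.
- That the difference favours apparent improvement, or is worth some number of points. Nothing in the documents gives a sign or a size.

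The conclusion assumes that sites follow Table 2 at Visits 1 and 9, and that Weeks 12 and 52 take place as site visits. Section 8.1.7 allows home completion when the pandemic makes a visit remote, which would add another setting.

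**What to change.** In Table 2, move the SBS-I, EQ-5D-5L and PGIC rows from Day 2 to Day 1, before any other assessment, at Visits 1 and 9 (PGIC at Visit 9 only). This is what footnote 15 and Section 8.2.17 already require. It changes three rows and adds no visit or questionnaire.

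If patients are already enrolled:

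- Anyone whose baseline was taken on Day 2 keeps Day 2 at Visit 9, so that the Week 24 change stays matched within the patient.
- Flag the actual PRO day in Listings 2-19 and 2-20.1 to 2-20.3.
- State the setting difference beside the Week 12 and Week 52 changes in the SAP and the trial report.

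The cost is a protocol table correction, a flag in four listings and a sentence of reporting text. The downside is mixed timing across patients if some already have a Day 2 baseline.

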# 2.2 Background

Patients with SBS are characterized by reduced intestinal absorptive surface area due to extensive surgical bowel resection or congenital diseases, such as recurrent Crohn's disease or mesenteric vascular disease (1,2,3,4), resulting in decreased absorptive capacity of the gut (5). This causes a reduced uptake of nutrients, fluids, electrolytes, vitamins, and trace elements, leading to difficulties with maintaining metabolic balances when receiving a conventional diet (6). The malabsorption can lead to dehydration, malnutrition, and weight loss if left untreated (7).

Less severely affected SBS patients are able to compensate for their malabsorption by increasing oral intake (hyperphagia) and adapt metabolically or pharmacologically. These patients suffer from intestinal insufficiency (SBS-II). More severely affected patients with intestinal failure (SBS-IF) depend upon the safe and well-adjusted provision of PS of nutrients, fluids, electrolytes, vitamins, and trace elements to maintain body function, growth, homeostasis, and health (8). For those dependent on PS, it is life-sustaining but at the same time associated with life-threatening complications. Among those are catheter-related blood stream infections or sepsis (9), central vein thrombosis, liver damage (10), and renal impairment (11). In addition, the treatment burden of PS is substantial. Often 10-28 liters of PS per week are required. In addition to 10- to 12-hour overnight PS infusions in such patients, additional hours during daytime may be required to compensate for losses. While liberating patients during daytime, night-time infusions disturb sleep and exacerbate the need for nocturnal urination. Adding to the treatment burden, patients on PS often need frequent follow-up checks at the hospital, and for many there is a need for help from a homecare nurse.

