# 8.2.1 Metabolic Balance Study

The metabolic balance study measures the total intake and output of energy, macronutrients (lipids, carbohydrates, proteins [nitrogen as a marker]) and micronutrients. The oral diet intake (i.e. food and fluids) are assessed by duplicate meals and liquids by quantification of weight, volume, as well as the content of energy, macronutrients and electrolytes. During the metabolic balance study, the patients will collect duplicate portions of all intake solid and liquid in buckets covering 24-hour periods. Likewise, all output (i.e. ostomy output, diarrhea and urine production) will be collected and quantified. The content of the buckets will be weighed, processed into dry matter by laboratory techniques and subsequently analyzed at the site's local laboratory.

Before the metabolic balance study is started, a fixed drinking menu will be set which will be followed for the metabolic balance study at Visits 1 and 9 (see Section 8.2.2).

The 48-hour metabolic balance study will start at 8:00 in the morning. If the patient receives PS at baseline, the 48 hours should preferably cover a day on PS (first day) and a day off PS.

The procedure for the metabolic balance study is listed below:

- The laboratory technician will inform the patient about collection of diet and liquid intake, urine and feces and hand out bottles and buckets that will be used for the collection.
- The collection will be performed for 48 hours.
- The patient will collect oral diet intake corresponding to the type and amount ingested. Wrapping paper, plum stones, chicken bones and similar will not be collected.
- Each day, bottles and buckets will be picked up by the laboratory technician.

Table 6 specifies the samples collected.

Table 6 Sample Collection during Metabolic Balance Study

| Sample             | To be collected in | Handling and storage               |
|--------------------|--------------------|------------------------------------|
| Urine              | Bottle             | No special handling or precautions |
| Feces              | Bucket             | Feces will be stored in a freezer  |
| Oral liquid intake | Bottle             | No special handling or precautions |
| Oral food intake   | Bucket             | No special handling or precautions |

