### 8.2.11 Body Weight

For both 48-hour metabolic balance studies an average of the two 24-hour days will be calculated. Changes from baseline to Week 12 (Visit 6), Week 24 (Visit 9) and Week 52 (Visit 12) will be measured. See also Section 8.1.3.

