### 8.2.12 Body Composition by DEXA

A DEXA scan shows the distribution of total body fat, lean body mass and bone mineral content and thus, also contributes as a safety assessment to determine if patients accumulate fluid as edema. DEXA is a low dose x-ray assessment equivalent to 1/10 of the dose of a regular x-ray examination of the thorax. Patients are exposed to less than 0.0005 mSv per scan. During the whole trial (4 DEXA-scans), the radiation dose is comparable to one day of natural background radiation (35). The radiation a patient is exposed to is considered low and is not associated with any known risk. A full DEXA scan takes approximately 20 minutes.

The total lean body mass, total fat mass, fat percent, total bone mineral content, bone mineral density as well as the T-score and Z-score will be measured using DEXA scan.

Changes from baseline to Week 12 (Visit 6), Week 24 (Visit 9) and Week 52 (Visit 12) will be measured.

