2.4 Exploratory Endpoints

Exploratory objectives are:

- To investigate the effect of treatment with glepaglutide on nutritional status, organ function and fluid balance
- To investigate the effect of treatment with glepaglutide on patient reported outcomes (PROs)
- To investigate the microbiome composition of subjects with SBS
- To investigate the pharmacokinetics of glepaglutide.

Exploratory endpoints are:

• Body weight: Change from baseline to Week 12, 24 and 52.

Body weight (kg) will be analyzed at Baseline, Week 12, Week 24 and Week 52 (EOT). The change of body weight (kg) from baseline to Week 12, Week 24 and Week 52 (EOT) is calculated as described in Section 2.1.2 and will be analyzed at Week 12, Week 24 and Week 52 (EOT).

• Body composition (lean body mass, fat mass and bone mineral content) by dual-energy X-ray absorptiometry (DEXA): Change from baseline to Week 12, 24 and 52.

The total lean body mass, total fat mass, fat percent, total bone mineral content, bone mineral density as well as the T-score and Z-score will be measured using DEXA scan.

During the whole trial, four DEXA scans will be performed: during the MBS at the baseline Visit (V1), at Week 12 (V6), during the MBS at Week 24 (V9) and at Week 52 (V12). During the MBS at V1 and V9, the DEXA scan may be done either on Day 2 or on Day 3.

The parameters

- Lean body mass (kg)
- Fat mass (kg)
- Bone mineral content (kg)

will be analyzed at Baseline, Week 12, Week 24 and Week 52 (EOT). Changes from baseline to Week 12, Week 24 and Week 52 (EOT) are calculated as described in Section 2.1.2 and will be analyzed at Week 12, Week 24 and Week 52 (EOT).

DEXA parameters fat percent, bone mineral density, T-score and Z-score will only be listed.

• Citrulline: Change from baseline to Week 12, 24 and 52.

Citrulline will be analyzed at Baseline, Week 12, Week 24 and Week 52 (EOT). Changes from baseline to Week 12, Week 24 and Week 52 (EOT) are calculated as described in Section 2.1.2 and will be analyzed at Week 12, Week 24 and Week 52 (EOT).

• Aldosterone: Change from baseline to Week 12, 24 and 52.

Aldosterone will be analyzed at Baseline, Week 12, Week 24, Week 52 (EOT). Changes from baseline to Week 12, Week 24 and Week 52 (EOT) are calculated as described in Section 2.1.2 and will be analyzed at Week 12, Week 24 and Week 52 (EOT).

• Estimated glomerular filtration rate (eGFR), creatinine clearance and liver function tests: Change from baseline to Week 12, 24 and 52.

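### In SBS-IF patients on parenteral support 1–6 days a week, DEXA scans and the Week 12 and 52 weights are not matched for infusion timing, so exploratory body-composition changes can include infused water

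*Protocol*

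**What the plan says.** **DEXA, Visits 1 and 9.** Protocol Section 1.2, Table 2 (balance-study flowchart), marks the scan on Day 2. Footnote 5 adds that the "DEXA scan may be done on Day 2 or Day 3 to allow for study site flexibility". SAP Section 2.4 repeats this: "During the MBS at V1 and V9, the DEXA scan may be done either on Day 2 or on Day 3". Neither document asks for the same day at both visits, and the SAP attaches no flag or sensitivity analysis.

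**PS status of those days.** Collection starts on Day 2. Protocol Section 8.2.1 says that, for a patient on PS at baseline, "the 48 hours should preferably cover a day on PS (first day) and a day off PS".

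**DEXA and fluid.** Protocol Section 8.2.12 says that the scan "contributes as a safety assessment to determine if patients accumulate fluid as edema".

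**Body weight.** At Visits 1 and 9 it is taken "at the same time point each day, in the morning prior to breakfast" (Table 2, footnote 1), and Section 8.2.11 states: "For both 48-hour metabolic balance studies an average of the two 24-hour days will be calculated". Section 8.1.3 applies at every visit: calibrated scale, light clothing, no shoes, stoma bag emptied. PS is not mentioned. Weights at Weeks 12 and 52 are single readings.

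**Contrast with other measurements.** Protocol Section 8.2.3 ties the 48-hour urine collection to the PS schedule. SAP Section 2.2.1 treats the on-PS and off-PS periods as not interchangeable and, for patients on PS, requires both before a balance value is used.

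**The concern.** Body weight and composition are the trial's measures of nutritional status, which is part of its stated purpose. Protocol Section 4.2 says that the long-term effect of reduced PS on weight and body composition is unknown. PS is therefore part of the question, and its infused water is also a source of error in the measurement.

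If a patient is scanned on an on-PS day at one visit and an off-PS day at the other, the lean-mass change includes whatever infused water was present at one scan and absent at the other. The same applies to scans at Weeks 12 and 52, when a patient may come straight from an overnight infusion: Protocol Section 5.3.1 allows PS during the fast required at those visits. With few SBS-IF patients, one mismatch can visibly move the subgroup mean.

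**Working it through.** The documents state no SD, error or expected change for DEXA or weight, so there is no planned figure to reproduce. The size of the possible artefact follows from the volume per infusion day.

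**Inputs**
- Weekly PS volume: 10–28 L. Protocol Section 2.2: "Often 10-28 liters of PS per week are required". This is background, not trial data.
- PS days per week: 1–6 for the day choice to matter. Patients on PS 7 days a week are measured on two PS days (Section 8.2.3).
- Retained share *f* at the time of measurement: not in the documents. Assumed 0.25, 0.50 and 0.75.
- SBS-IF patients: about 5, half of the 10 to be allocated (Section 9.2).

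**Volume per PS day**, V = weekly volume / PS days:
- 6 days: 10/6 = 1.67 L to 28/6 = 4.67 L
- 5 days: 10/5 = 2.0 L to 28/5 = 5.6 L

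Two values from this range are carried forward: 2.0 L and 4.67 L.

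**Shift in one patient's change** (1 L taken as 1 kg). A DEXA mismatch gives V × f. A single weight against a baseline mean of one on-PS and one off-PS reading gives V × f / 2, because the mean already holds half of V × f.

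| V (L) | f | DEXA mismatch, V × f (kg) | Single weight vs mean, V × f / 2 (kg) |
|---|---|---|---|
| 2.0 | 0.25 | 0.50 | 0.25 |
| 2.0 | 0.50 | 1.00 | 0.50 |
| 2.0 | 0.75 | 1.50 | 0.75 |
| 4.67 | 0.25 | 1.17 | 0.58 |
| 4.67 | 0.50 | 2.33 | 1.17 |
| 4.67 | 0.75 | 3.50 | 1.75 |

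**Effect on the SBS-IF mean**, n = 5, f = 0.50:
- One mismatched patient: 1.00/5 = 0.20 kg, or 2.33/5 = 0.47 kg.
- Day picked at random at each visit in all five, all on 1–6 PS days: added SE = V × f × √(0.5/5), which is 1.00 × 0.316 = 0.32 kg, or 2.33 × 0.316 = 0.74 kg.

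**Weight at Week 24.** If Visits 1 and 9 both average one on-PS and one off-PS reading, each mean carries V × f / 2 and the mismatch cancels, apart from any change in V.

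**What matching leaves.** The Section 8.2.9 example lowers PS from 10 to 8.6 L/week, a cut of 1.4 L. That is 1.4/7 = 0.20 L per PS day on 7 days or 1.4/5 = 0.28 L on 5 days. Times f, the residual is 0.05–0.15 kg or 0.07–0.21 kg; a larger cumulative cut scales it up.

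**The case against.** **Weights are standardised in other respects.** A reader might infer that the Week 12 and 52 weights are uncontrolled. They are not: Section 8.1.3 fixes scale, clothing and stoma bag, and both are fasting visits. The home scale in Section 8.1.7 is a pandemic contingency. Only PS timing is missing.

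**The litre figures are ceilings.** A reader might take the full infused volume as the error, or infer that it rivals the tissue change sought. Section 2.2 says that night infusions increase nocturnal urination, so water is lost as it is given. The documents state no expected lean-mass or weight change; the 5% weight criterion is an eligibility limit. Putting 28 L on very few days is a pairing that no section gives.

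**Day 2 may not be the post-infusion day.** With an overnight infusion and an 08:00 start, a daytime Day 2 scan can precede the infusion and a Day 3 scan follow it. This stands. It leaves the direction uncertain but not the difference between days, and it means that matching must refer to the last infusion as well as the day label.

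**Part is recoverable.** The diary holds infusion dates and volumes, the SAP lists diary, DEXA and visit data, and SBS-IF is tabulated separately. This helps with flagging but does not make the scans comparable. The diary items named in Section 8.2.4 do not include infusion clock time.

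**Falling PS volume.** A reader might infer a substantial downward bias from PS reduction alone. The direction is plausible for post-infusion measurements, but the protocol's own example supports only the small residual shown above.

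**Conclusion.** The gap is real but limited. It affects the exploratory DEXA changes of SBS-IF patients on PS 1–6 days a week, and their weight changes at Weeks 12 and 52. With retention assumed at 25–75%, a mismatched DEXA pair is off by 0.5–1.5 kg at 2.0 L per PS day and about 1.2–3.5 kg at 4.67 L. A single weight against the averaged baseline is off by about 0.25–0.75 kg or 0.6–1.75 kg. These ranges rest on the assumed retention and on the background PS volumes.

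The Week 24 weight change is largely protected by averaging at both visits. The protection is weaker for a patient on PS 7 days a week at baseline who has fallen below 7 by Visit 9. SBS-II results are free of the artefact. The endpoints are descriptive (SAP Section 4.3.4), so a reader should not infer any effect on the primary or key secondary tests. This is a cheap improvement to make, not a threat to the main conclusions.

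**What to change.** 1. **Protocol Table 2, footnote 5, and SAP Section 2.4.** Scan each SBS-IF patient on the same balance-study day, and at a similar time relative to the last infusion, at Visits 1 and 9. Note that time at the scan.
2. **Visits 6 and 12.** Where possible, schedule DEXA and weighing at the same point of the patient's existing PS cycle as the Visit 1 scan. The PS regimen itself is not changed.
3. **SAP, body weight.** Keep the two-day mean for the Week 24 change and state it in the SAP, whose Section 2.2.1 list of averaged items omits weight. For Weeks 12 and 52, compare with the Visit 1 weight from the day of matching PS status. Replacing the mean by a single day at Week 24 would discard averaging that already removes most of the mismatch.
4. **SAP, sensitivity summary.** Use diary infusion dates and volumes to flag unmatched DEXA and weight values, and flag any home-scale weights.

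**Cost.** Slightly less scheduling flexibility for the site; no extra scan or visit. Matching does not remove the smaller effect of reduced infusion volume, and it is not possible for a patient weaned off PS whose baseline was post-infusion. Those cases can only be flagged.
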